## 15.2 Secondary Safety Analyses

The secondary safety endpoints include the following:

- Rates of cumulative and persistent AEs in first operative eyes through Month 12 (Visit 5), compared to the ISO SPE rates as described in ISO 11979-7
- Visual disturbances using the QoV questionnaire and QoV Supplemental Questions at Month 12 (Visit 5)

The ISO defines cumulative adverse events as the “total number of adverse events that have occurred at any time up to a specified time point post-operatively” and a persistent adverse event as an “adverse event that is present at the conclusion of a clinical investigation”. Cumulative and persistent AEs from ISO 11979-7 Table E.2 will be summarized by AE and treatment group using discrete summary statistics separately for first operative eyes, second operative eyes, and all operative eyes. Cumulative AEs which occur at any time during the study will be counted. If a subject experiences a specific cumulative AE more than once during the study, they will only be counted once for that specific cumulative AE. Persistent AEs which are classified as ongoing at the time of study exit will be counted, and a subject will only be counted at most one time for a specific persistent AE.

The p-values from one-sided exact binomial tests comparing the observed AE rates to the SPE rates from Table E.2 will also be presented by treatment group. Additionally, cumulative and persistent adverse events will be summarized separately by age group (< 65 years vs. ≥ 65 years) and by site for first operative eyes, second operative eyes, and all operative eyes. The binomial test p-values will be computed as in the SAS® code below:

```
data ae_tbl;
  set ae_tbl;
  percent = 100*FREQ/N;
  pval = 1 - cdf('BINOMIAL', FREQ - 1, spe/100, N);
run;
```

where

- FREQ = number of unique eyes for each AE from ISO 11979-7 Table E.2

- $N$  = number of eyes in the Safety Set for each treatment group
- $spe$  = SPE rate for each AE from ISO 11979-7 Table E.2

The Quality of Vision (QoV) questionnaire will be used to assess subjective visual disturbances reported by subjects receiving IOLs. The QoV asks the subject to rate the frequency, severity, and degree of bothersomeness for 10 items/visual disturbances in their everyday life based on the past week. The rating scales for frequency, severity, and degree of bothersomeness are:

- Frequency: 0 (Never), 1 (Occasionally), 2 (Quite Often), 3 (Very Often)
- Severity: 0 (Not at all), 1 (Mild), 2 (Moderate), 3 (Severe)
- Bothersome: 0 (Not at all), 1 (A little), 2 (Quite), 3 (Very)

An example set of questions for the glare item/visual disturbance is provided below:

a) How often do you experience glare?  
Never    Occasionally    Quite often    Very often

b) How severe is the glare?  
Not at all    Mild    Moderate    Severe

c) How bothersome is the glare?  
Not at all    A little    Quite    Very

Scores for each subscale (frequency, severity, degree of bothersomeness) ranging from 0 to 100, with higher scores indicating a higher degree of visual disturbances, will be computed using a Rasch scoring algorithm which utilizes data from the original validation of the QoV.

The QoV Supplemental Questions will include the following questions:

1. How much trouble do you have with distance vision outdoors in daylight?
2. How much trouble do you have with distance vision outdoors at night or in dark situations?
3. How much trouble do you have with distance vision when indoors?
4. How much trouble do you have with near vision outdoors in daylight?
5. How much trouble do you have with near vision outdoors at night or in dark situations?
6. How much trouble do you have with near vision when indoors?
7. How much trouble do you have with blurred vision when looking at things in the distance?
8. How much trouble do you have with blurred vision when looking at things that are near?
9. How much trouble do you have with night vision?
10. How much trouble do you have with night driving?
11. How much trouble do you have with color disturbances?
12. If given the opportunity, would you again elect to be implanted with the same intraocular lens (IOL)?

The response options for questions 1 to 11 from the QoV Supplemental Questions will be "none," "a little," or "a lot." For question 12 regarding satisfaction with the IOL, responses of "yes" or "no" will be recorded.

The QoV Rasch subscale scores (frequency, severity, bothersomeness) will be summarized by treatment group using continuous summary statistics. As additional analyses of the QoV questionnaire, the categorical responses for each item at Month 12 (Visit 5) will be summarized by treatment group using discrete summary statistics.

The categorical responses from the QoV Supplemental Questions at Month 12 (Visit 5), including subjects' satisfaction with the IOL, will be summarized by treatment group using discrete summary statistics.

As poolability analyses, the secondary safety endpoints will be summarized by treatment group and site using discrete or continuous summary statistics as appropriate.

As subgroup analyses, the analyses of the rates of cumulative and persistent AEs through Month 12 (Visit 5) will be repeated for the following Pre-Operative Visit photopic pupil size subgroups: small (< 2.5 mm), medium (2.5 to  $\leq$  4mm), and large (> 4 mm). Similar subgroup analyses will be performed for visual disturbances using the QoV questionnaire and QoV Supplemental Questions at Month 12 (Visit 5) with subgroups based on photopic pupil size at Month 12 (Visit 5).

### **15.3 Adverse Events**

[figure not shown]
Adverse events (AEs) will be coded using MedDRA Version 24.1.

Non-ocular treatment-emergent adverse events (TEAE) include all AEs occurring or worsening during or after the first eye operation. Ocular TEAEs for a respective eye will include all AEs occurring or worsening during or after the operation for the respective eye.

TEAEs based on consensus definitions as set forth by the American Academy of Ophthalmology (AAO)'s Task Force will be summarized by treatment group using discrete summary statistics. Separate summaries will be provided for first operative eyes, second operative eyes, and all operative eyes.

An overall summary will be presented that includes the number and percentage of subjects who experienced at least one event by treatment group for the following AEs:

- TEAEs
- Ocular TEAEs
- Non-ocular TEAEs
- Treatment-emergent Serious Adverse Events (TE-SAEs)
- Ocular TE-SAEs
- Non-ocular TE-SAEs
- Ocular device-related TEAEs
- Ocular TEAEs by strongest relationship to study device
- Ocular TEAEs by strongest relationship to surgical procedure
- Ocular TE-SAEs by strongest relationship to study device
- Ocular TE-SAEs by strongest relationship to surgical procedure

- Ocular TEAEs of moderate to severe severity
- Ocular TEAEs by maximum severity
- Ocular TEAEs by study day of onset
- Ocular TEAEs by age group (< 65 years vs  $\geq$  65 years)
- Ocular TEAEs by pre-operative photopic pupil size (Small [ $<$  2.5 mm], Medium [2.5 to  $\leq$  4 mm], Large [ $>$  4 mm])
- Ocular TEAEs by site
- TEAEs leading to discontinuation from study
- TEAEs leading to death

For the summary of ocular TEAEs by pupil size, the average pupil size computed over both eyes will be used to determine the pupil size subgroup.

In addition, the following summaries by SOC, PT, and treatment group will be provided at eye level (first operative eyes, second operative eyes, and all operative eyes separately) or subject level as appropriate:

- Ocular TEAEs
- Non-ocular TEAEs
- Ocular TE-SAEs
- Non-ocular TE-SAEs
- Ocular TEAEs related to study device
- Ocular TEAEs related to surgical procedure
- Ocular TEAEs by maximal severity

In the summaries, SOCs are listed in alphabetical order, and PTs within an SOC are listed in order of descending frequency for FINEVISION HP treatment.

[figure not shown]
All AEs and all TE-SAEs will be presented in separate listings.

## 16. Additional Clinical Parameters

### 16.1 Visual Acuity (Early Treatment of Diabetic Retinopathy Study)

Actual values, changes from baseline, and changes between consecutive post-operative visits for photopic monocular logMAR BCDVA will be summarized using continuous summary statistics for each treatment group at each visit for each eye (first eye, second eye, and all eyes separately) for the Safety Set. Additionally, the numbers and percentages of subjects with changes greater than or equal to 0.20 logMAR (loss of at least 10 ETDRS letters) for changes from baseline and changes between consecutive post-operative visits will be presented by visit. Change between consecutive post-operative visits will be computed as the current visit minus the previous visit.

Subject listings of visual acuity variables will also be provided.

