## 4 STUDY DESIGN

## 4.1 OVERALL DESIGN

This study is a prospective, multicenter, randomized, active controlled, double masked pivotal study. It compares an investigational trifocal IOL, FINEVISION HP Trifocal IOL, and a commercially available monofocal IOL, AcrySof SN60AT [REDACTED] Monofocal IOL Model SN60AT [REDACTED] (Alcon). The study will include adult subjects with operable cataracts in both eyes who are eligible for phacoemulsification cataract surgery followed by IOL implantation. Potential subjects, after signature of the study informed consent document, will be screened for eligibility. Subjects who meet all protocol-specified eligibility criteria will be randomized at a 2:1 ratio to receive either the FINEVISION HP Trifocal IOL (test) or the AcrySof SN60AT [REDACTED] Monofocal IOL (control) in both eyes. The first eye undergoing cataract surgery/IOL implantation will be the eye with the worse preoperative BCDVA. If BCDVA of both eyes is the same, the first operative eye will be the right eye. Subjects will undergo cataract surgery/IOL implantation in the second operative eye 7 – 30 days subsequent to primary eye surgery. Subjects will attend regular visits where they will undergo ophthalmic examinations over a period of approximately 12 months.

Standard clinical trial methods will be used to minimize bias, such as the use of a masked vision assessor as well as masking of subjects, standardized test procedures, common investigator training and common inclusion and exclusion criteria. [REDACTED]

4.2

The purpose of this clinical study is to compare the visual

The purpose of this clinical study is to compare the visual outcomes and safety of the FINEVISION HP Trifocal IOL to that of the AcrySof Monofocal IOL Model SN60AT [REDACTED]. Visual outcomes evaluated will include distance, intermediate and near visual acuity. The study is designed to meet the requirements specified for multifocal IOLs in the ISO 11979-7, ISO 11979-9, and ANSI Z80.12 standards.

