#### 5.1 INCLUSION CRITERIA

Eligible subjects must meet all the following inclusion criteria in order to be eligible for study participation. Ocular criteria must be met for both eyes:

- 1) Male or female adults, age 22 years or older at the Preoperative Visit.
- 2) Visually significant cataracts in both eyes that are eligible for phacoemulsification cataract surgery.
- 3) Willing to undergo cataract surgery in the second operative eye within 7 – 30 days after surgery in the first eye.
- 4) Projected BCDVA of 0.2 logMAR (20/32 Snellen) or better in each eye after cataract surgery/IOL implantation, as determined by the medical judgement of the Investigator
- 5) Eligible for receipt of an IOL power within the range of the investigational IOL (+10.0 D to +30.0 D, in 0.50 D increments) in each eye
- 6) Contact lens users must be willing to discontinue wear of their lenses in accordance with the following requirements:
  - Rigid gas permeable lenses for  $\geq$  7 days prior to the Preoperative Visit
  - Soft contact lenses for  $\geq$  3 days prior to the Preoperative VisitContact lens wearers must demonstrate a stable refraction (within  $\pm 0.50$  D for both sphere and cylinder) in each eye, as determined by manifest refraction on two consecutive examination dates at least one week apart after discontinuation of contact lens wear.
- 7) Provide signed written consent prior to participation in any study-related procedures.

- 8) Ability, comprehension, and willingness to follow study instructions, and likely to complete all study visits.
- 9) Female subjects must be 1-year postmenopausal, surgically sterilized, or, if of childbearing potential, have a negative urine pregnancy test at the Preoperative Visit. Women of childbearing potential must use an acceptable form of contraception throughout the study. *Acceptable methods include at least one of the following: intrauterine (intrauterine device), hormonal (oral, injection, patch, implant, ring), barrier with spermicide (condom, diaphragm), or abstinence.*

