## 8.7.2 DEFINITION OF SERIOUS ADVERSE EVENTS

A serious adverse event (SAE) is defined as any untoward medical occurrence that meets any of the following:

- Is associated with a loss of 2 or more lines of BCDVA [loss of 10 or more Early Treatment Diabetic Retinopathy Study (ETDRS) letters] at Visit 4 or later from any prior postoperative visit
- Requires inpatient hospitalization or prolongation of existing hospitalization;
- Requires medical or surgical intervention to preclude permanent impairment of a body function or permanent damage to a body structure;
- Is life threatening (places the subject at immediate risk of death from the event as it occurred) or sight threatening;
- Results in permanent impairment of a body function or permanent damage to a body structure;
- Results in death;
- May jeopardize the subject and require medical or surgical intervention to prevent one of the other outcomes.

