### **Other Safety Endpoints**

YAG capsulotomy procedures (number and rate) will be summarized by descriptive statistics for each IOL group.

Other safety endpoints will be summarized descriptively by visit, including but not limited to IOP, slit lamp examination results, dilated fundus exam results, and PCO results. Changes or shifts from baseline will also be summarized where appropriate. In addition, the proportion of eyes with any worsening in BCDVA during the study of 10 letters or more (from a postoperative visit to any later postoperative visit) will be summarized. Reasons for VA worsening by 10 letters or more will be summarized. For assessments performed by eye, first operative eye and second operative eye will be summarized separately.

---

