### **8.3 Definition of Baseline**

Baseline will refer to measurements performed during the Pre-Operative Visit (Visit 0).

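### SAP 16.1 counts 10-letter BCDVA losses only against the preoperative eye or the visit just before, so it misses gradual postoperative losses that the protocol's safety summary would count

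*SAP*

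**What the plan says.** Three definitions of a 10-letter loss are in play.

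- **Protocol 9.4.6, Other Safety Endpoints.** The share of eyes showing "any worsening in BCDVA during the study of 10 letters or more (from a postoperative visit to any later postoperative visit) will be summarized". The next sentence adds a summary of the reasons.
- **Protocol 8.7.2, SAE definition.** A loss of two lines or 10 letters counts as serious when seen "at Visit 4 or later from any prior postoperative visit". The anticipated adverse event list in 8.7.7 uses the same comparison.
- **SAP 16.1.** It tabulates subjects with "changes greater than or equal to 0.20 logMAR (loss of at least 10 ETDRS letters"), and does so "for changes from baseline and changes between consecutive post-operative visits will be presented by visit". It then states: "Change between consecutive post-operative visits will be computed as the current visit minus the previous visit".

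SAP 8.3 fixes the reference for the first SAP comparison: "Baseline will refer to measurements performed during the Pre-Operative Visit (Visit 0"). SAP Section 1 says that its methods supersede those in the protocol, so the narrower count governs. The legible items of SAP Section 19 (changes from the protocol) do not mention this change.

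**The concern.** The threshold is the same in all three places, but the reference visit is not. A loss spread over two or three intervals can pass 10 letters in total while each step stays below 10, and the consecutive-visit count then records nothing.

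The baseline count seldom helps. Baseline is the eye before cataract surgery. Protocol 5.1 requires "Visually significant cataracts in both eyes that are eligible for phacoemulsification cataract surgery", and Protocol 4.1 adds: "The first eye undergoing cataract surgery/IOL implantation will be the eye with the worse preoperative BCDVA". A loss that stays within the gain from surgery still reads as an improvement from baseline.

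At stake is a sight-loss table for an implanted device that would understate gradual loss while capturing most abrupt loss. It would also use a different rule from the SAE definition, so it could not serve as a check on SAE reporting.

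**Working it through.** **Inputs from the documents**

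- Threshold: 10 letters. Protocol 8.7.2 equates two lines with 10 letters, and the SAP imputation code rounds acuity to 0.02 logMAR, which is one letter. So 10 × 0.02 = 0.20 logMAR, which reproduces the SAP cut-off.
- Scheduled postoperative BCDVA: Visits 2, 3, 4 and 5 (variable list in SAP 13.1).

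**Visit pairs compared**

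| Rule | Pairs | Covered by SAP consecutive rule |
|---|---|---|
| Protocol 9.4.6, any earlier to any later visit | 4 × 3 / 2 = 6 | 3 (V2–V3, V3–V4, V4–V5) |
| SAE definition, later visit is V4 or V5 | 2 + 3 = 5 | 2 (V3–V4, V4–V5) |

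The pairs never compared are V2–V4, V2–V5 and V3–V5.

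**Worked eyes**

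1. 0.00, 0.12, 0.24 at successive visits. The steps are 0.12 and 0.12, both below 0.20, so the eye is not counted. The total is 0.24 / 0.02 = 12 letters, so the protocol counts it. The baseline count would include it only if preoperative BCDVA was 0.24 − 0.20 = 0.04 or better.
2. 0.00, 0.00, 0.10, 0.20 at V2 to V5. The steps are 0, 5 and 5 letters, so it is not counted. V2 to V5 is 10 letters, which meets the protocol endpoint and the SAE acuity threshold. With an assumed preoperative value of 0.40, the change from baseline is 0.20 − 0.40 = −0.20, an improvement.
3. 0.00, 0.18, 0.36, 0.54 at V2 to V5. Each step is 9 letters and none is counted, although the eye has lost 27 letters. With an assumed preoperative value of 0.60 it is still 3 letters better than baseline.
4. 0.00, 0.00, 0.00, 0.20 at V2 to V5. The last step is 10 letters, so both rules count it.

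**Illustrative simulation**

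There were 400,000 eyes per scenario at V2 to V5, with independent normal measurement error at each visit and values rounded to 0.02 logMAR. The protocol rule is a later value minus the best earlier value of at least 0.20. The SAP rule is a consecutive difference of at least 0.20. The error SD (0.03 to 0.05 logMAR) and the patterns of loss are assumptions; the documents give neither. The baseline count is left out.

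| True pattern | Protocol rule flags | SAP consecutive rule flags |
|---|---|---|
| Steady 0.08 per visit (0.24 in total) | 82–89% | 1.5–18% |
| 0.12 + 0.12 between V3 and V5 | 90–96% | 10–32% |
| Abrupt 0.24 at V5 | 93–98% | 76–88% |
| Abrupt 0.30 at V5 | 99–100% | 94–99.5% |
| No true change, SD 0.05 | about 2% | about 1% |

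The two abrupt rows show that the gap belongs mainly to gradual loss. At the same total loss of 0.24, the consecutive rule finds 76–88% of abrupt losses but at most 32% of gradual ones.

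**The case against.** The strongest reply is that these losses do not vanish from the outputs. SAP 16.1 does not alter the SAE criterion, which the investigator applies. A reported loss enters the ocular SAE tables and listings of SAP 15.3. Acuity values are listed for each subject, and mean BCDVA is shown by visit. Posterior capsule opacification, YAG status, corneal edema and fundus findings have their own summaries. This stands as a limit on the consequence. It does not supply what the protocol promised, which is a count by arm from measured BCDVA, with reasons. The SAE route depends on reporting, and a loss first seen at Visit 3 falls outside the SAE acuity criterion.

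Other points stand in part:

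- The baseline count does catch an eye that ends 10 or more letters below its preoperative acuity. The protocol sets no minimum preoperative deficit, so the gap covers many gradual losses but not all.
- The simulation assumes that the eye has lost vision. It does not show how many of about 501 first eyes would be affected, and nothing in the documents gives that rate.
- The protocol's rule also flags more stable eyes by chance: about 2% against 1% at SD 0.05, and about 13% against 8% if the SD were 0.07.
- Part of SAP Section 19 is redacted and the table shells are not shown, so a declared change or an extra table cannot be excluded.
- The endpoint is descriptive. It carries no hypothesis test and cannot alter the effectiveness success rule.

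**Conclusion.** The concern holds. As far as the visible text goes, SAP 16.1 replaces the protocol's comparison between any two postoperative visits with a narrower one. It omits three of the six visit pairs and the summary of reasons. That follows from the text and needs no assumption.

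The size does rest on assumptions. For gradual losses of 0.24 logMAR with measurement SD 0.03 to 0.05, the consecutive rule flags about 1.5–32% of eyes against 82–96% under the protocol's rule. The number of eyes affected in this trial is unknown. The change should be made because it corrects a reported safety result, but the trial's main conclusions do not depend on it.

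**What to change.** In SAP 16.1, derive for each eye and each postoperative visit the BCDVA minus the best earlier postoperative BCDVA, and flag the eye if this reaches 0.20 logMAR at any visit. Report the number and percentage of eyes, with reasons, by arm for first, second and all operative eyes. Show the subset whose later visit is Visit 4 or 5, so that it can be set against reported SAEs. Keep the consecutive-visit table as an addition.

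State how missed visits and BCDVA from unscheduled visits enter the derivation, because the visible SAP does not say which visit counts as the previous one in those cases. If the narrower count is intended, declare it in Section 19 with a reason.

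The cost is one derived variable and one summary table. No new acuity assessments are needed. It is best settled before unmasking.

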## 16.2 Slit-Lamp Biomicroscopy Examination

A slit-lamp biomicroscopy examination will be performed for the eyelid, conjunctiva, cornea, anterior chamber, lens, and iris at each visit, except for the operative visits. Observations will be graded as Normal or Abnormal.

The results will be summarized using counts and percentages for each treatment group at each visit for each eye (first eye, second eye, and all eyes separately) using the Safety Set. Percentages will be based on the number of unique eyes in each treatment group with responses. Shift tables for the slit-lamp biomicroscopy parameters will also be provided comparing each follow-up visit to baseline for first operative eyes, second operative eyes, and all operative eyes separately.

[figure not shown]
Subject listings of the slit lamp biomicroscopy examination results will also be provided.

## 16.3 Anterior Chamber Cells and Flare

Anterior chamber cells and flare assessments will be performed at each visit, except for the operative visits. Cells and flare will be graded according to the scales described in Table 2 and Table 3, respectively.

**Table 2. Anterior Chamber Cells Grading Scale**

Grade	Cells in Field (Field is a 1x1 mm slit beam)
0	<1
0.5+	1-5
1+	6-15
2+	16-25
3+	26-50
4+	>50

